### 6.7.5 Management of eGFR Decreases

If calculated eGFR is confirmed to have decreased to  $< 50$  mL/minute, medical evaluation should include a full review of current medications, including those taken on an as needed basis, those which are sold over the counter and any dietary and herbal supplements, and appropriate dose reduction or discontinuation based on impaired renal function should be done (if applicable). Ribavirin dose should be adjusted as in [Table 15](#). Alternative management of RBV dose in the setting of reduced renal function will require approval of the AbbVie Study Designated Physician.

The investigator should also consider whether drug-drug interactions with concomitant medications may have contributed to the decrease in eGFR, and whether discontinuation of substitution of the possible interacting drug should be considered. For example, drug interactions between DAAs and some antihypertensive medications could potentially increase exposures of the antihypertensive and may reduce renal function. If anti-hypertensive medications are adjusted, vital signs must be monitored to ensure appropriate blood pressure control. Refer to Section 5.2.3.3 for additional information regarding drug-drug interactions.

If eGFR improves, the site should perform all necessary readjustment of any dose modifications that have been made.

The Investigator should ensure that any concomitant medication changes, RBV dose reductions, and study drug discontinuations, as well as consequent related adverse events are entered into the appropriate eCRFs.

**Table 15. Dosing of RBV in Subjects with Renal Impairment**

eGFR Value	RBV Dose
30 – 50 mL/min	Alternating doses of 200 mg with 400 mg every other day
< 30 mL/min	200 mg daily
Hemodialysis	200 mg daily

## 7.0 Protocol Deviations

The investigator should not implement any deviation from the protocol without prior review and agreement by the Sponsor and in accordance with the Independent Ethics Committee (IEC)/Independent Review Board (IRB) and local regulations, except when necessary to eliminate an immediate hazard to study subjects. When a deviation from the protocol is deemed necessary for an individual subject, the investigator must contact the following AbbVie personnel:

Primary Contact:

Alternate Contact:

Such contact must be made as soon as possible to permit a review by AbbVie to determine the impact of the deviation on the subject and/or the study. Any significant protocol deviations affecting subject eligibility and/or safety must be reviewed and/or approved by the IEC/IRB and regulatory authorities, as applicable, prior to implementation.

## **8.0 Statistical Methods and Determination of Sample Size**

### **8.1 Statistical and Analytical Plans**

An interim analysis will occur after all enrolled subjects from S. Korea and Taiwan have completed the Treatment Period through Post-Treatment Week 12 of the Post-Treatment Period or prematurely discontinued from the study. This interim analysis is planned to support regulatory submission activities in S. Korea and Taiwan. The primary analysis will occur after all subjects have completed PT Week 24 or prematurely discontinued the study. All remaining data through PT Week 48 will be summarized in the end of study analysis.

SAS® (SAS Institute, Inc., Cary, NC) for the UNIX operating system will be used for all analyses. All confidence intervals will be 2-sided with an  $\alpha$  level of 0.05. Descriptive statistics will be provided, such as the number of observations (N), mean, and standard deviation (SD) for continuous variables and counts and percentages for discrete variables.

Efficacy, safety, and demographic analyses will be performed on the intent-to-treat (ITT) population which will consist of all enrolled subjects who receive at least one dose of study drug. Additional summaries will be provided by geographic region (China, S. Korea, Taiwan).

No data will be imputed for any efficacy or safety analyses except for the PRO questionnaires and for analyses of the HCV RNA endpoints of RVR, EOTR, and all SVR endpoints. If a respondent answers at least 50% of the items in a multi-item scale of the SF-36v2, the missing items will be imputed with the average score of the answered items in the same scale. In cases where the respondent did not answer at least 50% of the items, the score for that domain will be considered missing. The Mental and Physical Component Summary measures will not be computed if any domain is missing. If a respondent answers at least 12 of the 16 items on the HCVPRO, the missing items will be imputed with the mean score of the answered items. In cases where the respondent did not answer five or more items, the HCVPRO total score will be considered missing. For EQ-5D-5L index and VAS scores, no imputation will be performed for missing items.

HCV RNA values will be selected for the analyses of HCV RNA endpoints of RVR, EOTR, and all SVR endpoints based on the defined visit windows. When there is no HCV RNA value in a visit window based on defined visit windows, the closest values before and after the window, regardless of the value chosen for the subsequent and preceding window, will be used for the flanking imputation described below.

If a subject has a missing HCV RNA value at a post-baseline visit but with undetectable or unquantifiable HCV RNA levels at both the preceding value and succeeding value, the HCV RNA level will be considered undetectable or unquantifiable, respectively, at this visit for this subject. Subsequent to this flanking imputation, if a subject is missing a value for the visit window associated with the analysis, the subject will be imputed as a visit failure (i.e., not undetectable or unquantifiable). For SVR analyses (e.g., SVR4, SVR12, SVR24) if after performing the flanking imputation there is no value in the appropriate window but there is an HCV RNA value after the window, then it will be imputed into the SVR window.

### 8.1.1 Demographics

Demographics and baseline characteristics will be summarized for the ITT population. Demographics include age, weight, and BMI, and the frequency of gender, race, ethnicity, age category ( $< 55$  years or  $\geq 55$  years] and [ $< 65$  or  $\geq 65$  years]) and BMI category ( $< 30$  kg/m^2 or  $\geq 30$  kg/m^2). Baseline characteristics will include IL28B genotype ([CC, CT, or TT] and [CC or non-CC]), IFN based therapy (IFN [alpha, beta or pegIFN] with RBV) treatment history (treatment-naïve or treatment-experienced) non-responder {null responder, partial responder, or other non-responder} or relapser or IFN based therapy intolerant, baseline HCV RNA levels ([continuous] and [ $< 800,000$  IU/mL or  $\geq 800,000$  IU/mL]), baseline IP-10 ([continuous] and [ $< 600$  pg/mL or  $\geq 600$  pg/mL]), baseline HOMA-IR ( $< 3$  mU  $\times$  mmol/L or  $\geq 3$  mU  $\times$  mmol/L), Child-Pugh score at Screening (5 or 6), baseline Child-Pugh score (5, 6, or  $> 6$ ), baseline longitudinal FibroTest score (continuous), baseline platelet counts [(continuous) and ( $< 60$ , 60 to  $< 90$ , 90 to  $< 120$ , or  $\geq 120 \times 10^9$ /L)], baseline albumin [(continuous) and ( $< 28$ , 28 to  $< 33$ , 33 to  $< 40$ , 40 to 49, and  $> 49$  g/L)], baseline alpha fetoprotein (continuous), presence of hepatic steatosis at baseline (yes, no), hepatoprotective drug use at baseline (yes, no), tobacco (user, ex-user, or non-user) and alcohol use (drinker, ex-drinker, or non-drinker) status, former injection drug user (yes, no, unknown), history of bleeding disorders (yes, no), history of diabetes (yes, no), history of depression or bipolar disorder (yes, no), and geographic region (China, S. Korea and Taiwan). Summary statistics (N, mean, median, Standard Deviation [SD], and range) will be generated for continuous variables (e.g., age and BMI). The number and percentage of subjects will be presented for categorical variables (e.g., gender and race).

### 8.1.2 Efficacy

All efficacy analyses will be performed on the ITT population.

Plasma HCV RNA levels will be determined for each sample collected by the central laboratory using the Roche COBAS TaqMan® real-time reverse transcriptase-PCR (RT PCR) assay version 2.0. For this assay, the lower limit of detection (LLOD) is 15 IU/mL

and lower limit of quantification (LLOQ) is 25 IU/mL. HCV RNA results that are detectable but not quantifiable are reported as "< 25 IU/ML HCV RNA detected" and those that are undetectable are reported as "HCV RNA not detected" in the database.

### **8.1.2.1 Primary Efficacy Endpoints**

For South Korea and Taiwan the primary endpoint is:

- A1. SVR12: Superiority to the historical SVR rate for telaprevir plus pegIFN/RBV therapy; the LCB of the 95% CI for the percentage of subjects with SVR12 must exceed 67% to achieve superiority.

For China, the primary endpoints are:

- B1. SVR12: Superiority to the historical SVR rate for telaprevir plus pegIFN/RBV therapy; the LCB of the 95% CI for the percentage of subjects with SVR12 must exceed 67% to achieve superiority.
- B2. SVR24: Superiority to the historical SVR rate for telaprevir plus pegIFN/RBV therapy; the LCB of the 95% CI for the percentage of subjects with SVR24 must exceed 67% to achieve superiority.

For China, in order to control the Type I error rate at 0.05, a fixed-sequence testing procedure will be used to proceed through the primary efficacy endpoints. That is, only if success has been demonstrated for the primary endpoint of superiority of SVR12 rate to the historical rate for telaprevir plus pegIFN and RBV therapy (B1) will the testing continue to the second primary endpoint of superiority of the SVR24 rate to the historical rate for telaprevir plus pegIFN and RBV therapy (B2).

To test the hypothesis that the percentage of treatment-naïve and IFN based therapy (IFN [alpha, beta or pegIFN] with RBV) treatment-experienced HCV genotype 1b infected Asian subjects with compensated cirrhosis treated with ABT-450/r/ABT-267 + ABT-333 + RBV for 12 weeks who achieve SVR12 is superior to a clinically meaningful threshold

based on the historical SVR rates for the HCV genotype 1 infected population treated with telaprevir plus pegIFN/RBV, the percentage of subjects with SVR12 will be calculated with a 2-sided 95% CI using Wilson score method, and the LCB will be compared to the defined threshold. The LCB of the 95% CI of SVR12 must be greater than 67% in order for the regimen to be considered superior.

Similarly, to test the hypothesis that the percentage of treatment-naïve and IFN based therapy (IFN [alpha, beta or pegIFN] with RBV) treatment-experienced HCV genotype 1b infected Asian subjects with compensated cirrhosis treated with ABT-450/r/ABT-267 + ABT-333 + RBV for 12 weeks who achieve SVR24 is superior to a clinically meaningful threshold based on historical SVR rates for the HCV genotype 1 infected population treated with telaprevir plus pegIFN and RBV, the percentage of subjects with SVR24 will be calculated with a 2-sided 95% CI using Wilson score method, and the LCB will be compared to the defined threshold. The LCB of the 95% CI of SVR24 must be greater than 67% in order for the regimen to be considered superior.

The value of 67% used in the endpoints as the historical SVR rate for telaprevir plus pegIFN/RBV is described in Section 5.6.3.

### 8.1.2.2 Secondary Efficacy Endpoints

The secondary efficacy endpoints are:

- The percentage of subjects with on-treatment virologic failure defined as the occurrence of at least one of the following:
  - confirmed HCV RNA  $\geq$  the lower limit of quantitation (LLOQ) (defined as 2 consecutive HCV RNA measurements  $\geq$  LLOQ) at any point during treatment after HCV RNA  $<$  LLOQ, or
  - confirmed increase from nadir in HCV RNA (defined as 2 consecutive HCV RNA measurements  $> 1 \log_{10}$  IU/mL above nadir) at any time point during treatment, or
  - Failure to achieve HCV RNA  $<$  LLOQ by Week 6 with  $\geq 36$  days of treatment.

- The percentage of subjects with relapse by Post-Treatment Week 12 (confirmed HCV RNA  $\geq$  LLOQ between end of treatment and 12 weeks after the last dose of study drug among subjects completing treatment and with HCV RNA  $<$  LLOQ at the end of treatment).
- The percentage of subjects with relapse by Post-Treatment Week 24 (confirmed HCV RNA  $\geq$  LLOQ between end of treatment and 24 weeks after the last dose of study drug among subjects completing treatment and with HCV RNA  $<$  LLOQ at the end of treatment).

The percentages (with 2-sided 95% confidence intervals using the Wilson Score method to the binomial distribution) of the subjects with on treatment virologic failure and post-treatment relapse will be calculated and summarized.

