- The percentage of subjects with SVR24 weeks after the last planned dose of study drug (SVR24planned);
- Mean change from baseline in liver function tests (e.g., PT/INR, Fibrotest) to each applicable post-baseline time point.

In the above analyses for RVR, EOTR, and SVR, the percentage of responders and 2-sided 95% confidence intervals using Wilson score method will be calculated. From HCV RNA levels, the time to suppression on treatment and time to relapse post-treatment will be displayed graphically using Kaplan-Meier curves.

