## **8.2 Determination of Sample Size**

It is planned to enroll approximately 100 subjects (60 from China, 20 from South Korea and 20 from Taiwan). All subjects will receive ABT-450/r/ABT-267 + ABT-333 coadministered with RBV for 12 weeks. With a total sample size of about 100 subjects and assuming that 94% of the subjects will achieve  $SVR_{12}$ , this study has greater than

90% power to demonstrate SVR12 superiority with a 2-sided 95% lower confidence bound greater than 67% (based on the normal approximation of a single binomial proportion in a one-sample test for superiority using EAST 6.2). The SVR24 rate is anticipated to be very similar to the SVR12 rate and thus the power should still be at least 90%. No adjustment for dropout is applicable because subjects who do not have data at Post-Treatment Week 12 (after imputing) are counted as failures for SVR12 and SVR24.

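### Both relapse percentages count completers with no post-treatment HCV RNA as not relapsed by default, which biases these secondary estimates slightly downward

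*Protocol*

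**What the plan says.** Section 8.1.2.2 gives two relapse endpoints. The first counts confirmed HCV RNA at or above LLOQ "between end of treatment and 12 weeks after the last dose of study drug among subjects completing treatment and with HCV RNA" below LLOQ at end of treatment. The second counts the same event "between end of treatment and 24 weeks after the last dose of study drug among subjects completing treatment and with HCV RNA" below LLOQ at end of treatment. The synopsis repeats both denominators. Each percentage gets a two-sided 95% Wilson interval.

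On missing data, Section 8.1 states: "No data will be imputed for any efficacy or safety analyses except for the PRO questionnaires". The one further exception it lists covers RVR, EOTR and SVR. Relapse is not among the exceptions. For SVR, after the flanking step, "if a subject is missing a value for the visit window associated with the analysis, the subject will be imputed as a visit failure", unless a later value can be moved into the window. Section 8.2 relies on this rule: "subjects who do not have data at Post-Treatment Week 12 (after imputing) are counted as failures".

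Section 8.1.2.5 lists time to relapse among the additional endpoints and says that "time to relapse post-treatment will be displayed graphically using Kaplan-Meier curves".

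**The concern.** The denominator depends only on status at end of treatment, while the numerator depends on what is seen afterwards. Nothing connects the two. A completer who is suppressed at end of treatment and never sampled again is in the denominator, has no value that could show relapse, and has none imputed. That subject lowers the relapse percentage exactly as an observed relapse-free subject would. A completer last seen at Post-Treatment Week 12 does the same to the Week 24 percentage.

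Missing data thus count against the regimen for SVR and in its favour for relapse. On-treatment failure and relapse are the only secondary efficacy endpoints and carry the secondary objective in Section 4.2. Few events are expected, so the Wilson upper limit tells the reader more than the point estimate does, and subjects with no data make that limit look tighter than the observations support.

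**Working it through.** **Three kinds of completer suppressed at end of treatment, under the rules as written**

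| Subject | SVR12 | SVR24 | Relapse by Week 12 | Relapse by Week 24 |
|---|---|---|---|---|
| No post-treatment value | failure | failure | in denominator, not an event | in denominator, not an event |
| Below LLOQ at Post-Treatment Week 12, then lost | success | failure | correctly observed, no event | in denominator, not an event |
| Below LLOQ through Post-Treatment Week 24 | success | success | observed, no event | observed, no event |

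The second row matters only for Week 24. Subjects who stop treatment early are outside the relapse denominator; Section 8.1.2.5 takes completion to be at least 77 days of study drug.

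**The plan's own figures.** The protocol states no expected relapse rate or loss rate. Its only sample size figure is power above 90% for SVR12 (Section 8.2: N = 100, true rate 94%, threshold 67%). By the normal approximation:

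(0.27 × √100 − 1.96 × √(0.67 × 0.33)) / √(0.94 × 0.06) = (2.70 − 0.92) / 0.237 ≈ 7.5

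Power is above 99.99%, consistent with the statement. The relapse denominator plays no part in this.

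**Size of the bias.** Let D be completers suppressed at end of treatment, m those with no post-treatment value, and R observed relapses.

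- As written: R / D.
- Observed only: R / (D − m).
- Ratio: (D − m) / D = 1 − m/D, so the relative understatement is m/D.

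Assume D = 95, R = 2, and m = 2 or 5. Wilson 95% intervals:

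| Denominator | Estimate | 95% CI |
|---|---|---|
| As written, 2/95 | 2.1% | 0.6 to 7.4 |
| m = 2, 2/93 | 2.2% | 0.6 to 7.5 |
| m = 5, 2/90 | 2.2% | 0.6 to 7.7 |

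The relative understatement is 2/95 = 2.1% for m = 2 and 5/95 = 5.3% for m = 5. With no relapses the point estimate stays at 0%, and for m = 5 the upper limit moves from 3.9% (0/95) to 4.1% (0/90).

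For scale, if all 5 unobserved subjects had relapsed, the rate would be 7/95 = 7.4% (3.6 to 14.4). That is an outer bound on what the data leave open, not an expectation.

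The ratio is exact for subjects with no post-treatment value. For those lost between Weeks 12 and 24, only relapses arising after their last sample are missed, so the effect per subject is smaller. Removing them altogether would discard real follow-up; a censored estimate is the natural comparator.

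**The case against.** The strongest reply is that whether a subject needs a post-treatment value to be evaluable is a detail for the SAP, which is not shown and may already require it. That would answer a protocol that was silent. This one fixes the denominator and separately bars imputation for relapse, so an SAP adding the requirement would be changing a stated secondary endpoint.

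The reply on size stands. The shift is a fraction of a percentage point, and the assumed losses are probably generous. In the 12-week arm of Study M13-099 (Section 3.0), 91.8% SVR12 among 208 subjects leaves about 17 failures, of which 13 were virologic. That leaves about 4/208 = 1.9% for every other reason, including early discontinuations that fall outside the relapse denominator. On that basis, 2 of 95 is more realistic than 5. The relapse endpoints are also descriptive: no test or threshold depends on them.

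Three stronger readings are tempting, and the protocol does not support them.

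- A reader might infer that the plan declares a lost subject relapse-free. It never labels such a subject; the result follows by default from the denominator.
- A reader might infer that the percentage and the Kaplan-Meier analysis give two incompatible relapse estimates. Section 8.1.2.5 plans only a graph. A crude proportion and a censored curve handle the same subjects differently, but no two reported figures contradict each other.
- A reader might point to Study M13-099, where 12 of 13 virologic failures in the 12-week arm were relapses, to argue that relapse will matter greatly here. That arm mixed genotypes 1a and 1b, and Section 3.0 attributes the lower response largely to genotype 1a prior null responders. This trial enrols genotype 1b only, for which Section 3.2 cites SVR12 of 100% and 98%.

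**Conclusion.** The point holds as a small, one-directional bias in two descriptive secondary endpoints. Against an observed-only denominator, the relapse percentage is understated by a relative m/D. For an assumed 2 to 5 unobserved among 95, with 2 relapses, that is 2.1% against about 2.2%, and an upper limit of 7.4% against 7.5% to 7.7%. Both the losses and the number of relapses are assumptions, since the protocol gives neither. The direction does not depend on them: the denominator as written can never overstate relapse relative to the observed-only rate.

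It would be wrong to infer that the primary conclusion is at risk. The SVR endpoints already count subjects with missing data as failures, and neither the 67% comparison nor its power uses the relapse denominator. The point is worth correcting because the remedy is simple and uses data already planned.

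**What to change.** In Section 8.1.2.2 and the synopsis, limit both relapse denominators to completers with HCV RNA below LLOQ at end of treatment who have at least one post-treatment HCV RNA value, and report how many are excluded for having none.

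That wording still keeps a subject lost between Post-Treatment Weeks 12 and 24 in the Week 24 denominator as not relapsed. So also report the Kaplan-Meier relapse estimate with its 95% CI at 12 and 24 weeks, from the time-to-relapse analysis already in Section 8.1.2.5, censoring at the last HCV RNA value.

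While the section is open, state how a single post-treatment value at or above LLOQ followed by loss is counted. Section 8.1.2.5 counts the on-treatment equivalent as rebound, but relapse needs two consecutive values (Section 5.1.3) and has no matching rule.

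The cost is a short text change and two extra estimates. No new visits, samples or subjects are needed. The reported relapse rate becomes slightly less favourable.

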### **5.1.3 Post-Treatment (PT) Period**

All subjects who receive at least one dose of DAA in the Treatment Period and either complete treatment or prematurely discontinue study drug will be monitored in the Post-Treatment Period for safety, HCV RNA, the emergence and persistence of resistant viral variants and assessment of PROs for an additional 48 weeks following the last dose of study drug.

The Post-Treatment Period will begin the day following the last dose of study drug treatment. Subjects with HCV RNA < LLOQ at the end of treatment and who have a confirmed HCV RNA  $\geq$  LLOQ (defined as 2 consecutive HCV RNA measurements  $\geq$  LLOQ) at any point in the Post-Treatment Period will be considered to have relapsed. Confirmation of an HCV RNA  $\geq$  LLOQ in the Post-Treatment Period should be completed as soon as possible.

Subjects who prematurely discontinue the Post-Treatment Period should return to the site for a Post-Treatment discontinuation visit as outlined in Table 6.

All subjects who receive at least one dose of DAA and who do not achieve and maintain virologic suppression (HCV RNA < LLOQ), or who relapse post DAA therapy, should discuss the future treatment options with the investigators.

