Following enrollment, the site will use the IRT system to obtain the study drug kit numbers to dispense at the study visits indicated in Section 5.5.7. Study drug must not be dispensed without contacting the IRT system. Study drug may only be dispensed to subjects enrolled in the study through the IRT system. At the end of the Treatment Period or at the Premature D/C Visit from the Treatment Period, the site will contact the IRT system to provide visit date information and study drug return information for each kit (Section 5.5.7).

All subjects who receive at least one dose of DAA and who fail to achieve virologic suppression, or who experience virologic breakthrough on DAA therapy will be discontinued from treatment. Resistance monitoring will continue in the Post-Treatment Period regardless whether subjects opt for alternative post-study treatment.

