#### **8.1.2.3 Sensitivity Analyses for the Primary Endpoint**

In addition to presenting the primary efficacy endpoints with HCV RNA and SVR12 and SVR24 imputed as described in Section 8.1, SVR12 and SVR24 will be presented using the following other methods to impute missing post-treatment virologic results:

- Imputing any missing HCV RNA values in the SVR12/SVR24 window by carrying forward the last non-missing (post-baseline) HCV RNA value prior to the SVR12/SVR24 window;
- Imputing as described in Section 8.1 but exclude the subjects who were categorized as "prematurely discontinued study drug with no on-treatment virologic failure" and "missing follow-up data in the PT Period."

For each of these, the simple percentage of subjects with SVR12/SVR24 will be presented along with a 2-sided 95% CI using Wilson score method.

As a sensitivity analysis, comparisons of the SVR12 and SVR24 rates may be made to geographic region-specific SVR rates with IFN based therapy (IFN [alpha, beta or pegIFN] with RBV) treatment.

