#### **8.1.2.5 Additional Efficacy Endpoints**

The following additional efficacy endpoints will be summarized and analyzed, as specified:

- The percentage of subjects with rapid virologic response (RVR) (HCV RNA  $< \text{LLOQ}$  at Week 4);
- The percentage of subjects with end of treatment response (EOTR) (HCV RNA  $< \text{LLOQ}$  at Week 12);
- The percentage of subjects with HCV RNA  $< \text{LLOQ}$  at each post-baseline visit in the Treatment Period (using only subjects with data in each visit window, i.e., no imputation for missing data);
- The number of subjects with virologic rebound at each protocol-specified visit (confirmed HCV RNA  $\geq \text{LLOQ}$  after HCV RNA  $< \text{LLOQ}$  during treatment, or confirmed increase from nadir in HCV RNA (two consecutive HCV RNA measurements  $> 1 \log_{10}$  IU/mL above nadir) at any time point during treatment. A single rebound value ( $\geq \text{LLOQ}$  or  $> 1 \log_{10}$  IU/mL above nadir) followed by lost to follow-up will be considered a rebound);
- The percentage of subjects who failed to have confirmed suppression of HCV RNA (never achieving HCV RNA  $< \text{LLOQ}$ ) during the Treatment Period and have received at least 6 weeks of treatment (study drug duration  $\geq 36$  days);
- Time to suppression of HCV RNA (defined as the study day of the first occurrence of HCV RNA  $< \text{LLOQ}$ ) during the Treatment Period;
- the percentage of subjects achieving  $\text{SVR}_4$ ;
- The percentage of subjects who complete treatment (defined as a study drug duration  $\geq 77$  days) with HCV RNA  $< \text{LLOQ}$  at Final Treatment Visit who relapsed post-treatment within 4 weeks after the last actual dose of study drug (up to and including the  $\text{SVR}_4$  assessment time point);
- The percentage of subjects who complete treatment (defined as a study drug duration  $\geq 77$  days) with HCV RNA  $< \text{LLOQ}$  at Final Treatment Visit who

relapsed between end of treatment and up to and including the last HCV RNA measurement collected in the PT Period;

- The percentage of subjects who achieved SVR24 who subsequently relapsed;
- Time to relapse at any time post-treatment for subjects who complete treatment with HCV RNA < LLOQ at Final Treatment Visit;
- The percentage of subjects with SVR12 weeks after the last planned dose of study drug (SVR12planned);
- The percentage of subjects with SVR24 (South Korea and Taiwan);

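### Relapse endpoints leave out confirmed relapse after early stopping, and the SVR rules do not exclude HCV RNA values obtained on another anti-HCV regimen

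*Protocol*

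**What the plan says.** **Relapse.** Section 5.1.3 states that a subject with HCV RNA below LLOQ at end of treatment and a confirmed value at or above LLOQ "at any point in the Post-Treatment Period will be considered to have relapsed". Section 5.4.1.1 repeats this. Neither sets a completion condition. Section 5.1.3 also says that subjects who "either complete treatment or prematurely discontinue study drug will be monitored in the Post-Treatment Period", so early stoppers are followed for relapse.

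Section 8.1.2.2 and the synopsis limit both relapse endpoints (post-treatment Weeks 12 and 24) to subjects "12 weeks after the last dose of study drug among subjects completing treatment and with HCV RNA" below LLOQ at end of treatment. The additional relapse rates in Section 8.1.2.5 carry the same limit ("The percentage of subjects who complete treatment (defined as a study drug duration" of at least 77 days). Section 4.2 makes on-treatment failure and post-treatment relapse the two measures of the secondary objective.

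**SVR.** Section 5.3.3.1 defines SVR12 and SVR24 only by HCV RNA below LLOQ 12 or 24 weeks after the last actual dose. Section 8.1 adds flanking imputation. If the SVR window is still empty "but there is an HCV RNA value after the window, then it will be imputed into the SVR window". Section 5.2.3.3 bars other anti-HCV drugs during the Treatment Period only. Section 5.5.1 foresees other therapy afterwards: "Resistance monitoring will continue in the Post-Treatment Period regardless whether subjects opt for alternative post-study treatment". Section 5.3.1.1 has post-treatment HCV antivirals recorded in the eCRF, and Table 6 continues HCV RNA sampling to post-treatment Week 48.

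**The concern.** The two secondary measures should together describe virologic failure. As defined they leave a gap: confirmed relapse in someone who stopped early while suppressed. The protocol's general definition calls this relapse, but its endpoints do not count it.

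The second issue reaches the primary variable. A subject who relapses and is then suppressed by a different regimen has not responded to the study regimen, yet no rule keeps that later value out of SVR. SVR24 is a primary endpoint for China, and it is more exposed than SVR12 because there is more time for another therapy to start and act.

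**Working it through.** **1. Relapse: tracing one subject.** The subject stops at Week 6 with HCV RNA below LLOQ and has two consecutive values at or above LLOQ by post-treatment Week 8.

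- Sections 5.1.3 and 5.4.1.1: relapsed.
- On-treatment failure (8.1.2.2): no.
- Relapse by Week 12 or Week 24 (8.1.2.2): not in the denominator.
- Additional relapse rates (8.1.2.5): excluded, since duration is under 77 days.
- SVR12 (8.1, ITT): non-responder.
- One sensitivity analysis in 8.1.2.3 removes subjects categorised as "prematurely discontinued study drug with no on-treatment virologic failure", a label that fits this subject.

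**Size.** The protocol gives no relapse rate by completion status, so the counts below are assumptions: 100 dosed, all suppressed at their final treatment visit, 2 completers relapse. The only related figure in the protocol is the 1.9% who discontinued for adverse events in the 12-week cirrhosis arm (Table 2). Brackets are Wilson 95% intervals.

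| Early stoppers | Of whom relapse | Endpoint as written | General definition |
|---|---|---|---|
| 2 | 1 | 2/98 = 2.0% (0.6 to 7.1) | 3/100 = 3.0% (1.0 to 8.5) |
| 5 | 2 | 2/95 = 2.1% (0.6 to 7.4) | 4/100 = 4.0% (1.6 to 9.8) |
| 5 | 5 | 2/95 = 2.1% (0.6 to 7.4) | 7/100 = 7.0% (3.4 to 13.7) |
| 5 | 0 | 2/95 = 2.1% | 2/100 = 2.0% |

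**2. SVR: tracing one subject.** The subject completes treatment suppressed, has confirmed relapse at post-treatment Week 8, starts another regimen, misses Week 12, and is below LLOQ at Week 24 on that regimen.

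- SVR24 (5.3.3.1): responder.
- SVR12: flanking does not apply, because the preceding value is quantifiable. The later-value rule in 8.1 then moves the Week 24 value into the empty window: responder.
- Relapse by Week 12 (8.1.2.2): relapsed.

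The primary and secondary endpoints then contradict each other for the same subject. Flanking has the same weakness where both neighbouring values were obtained on the new regimen.

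**The plan's own power figure.** Section 8.2 states more than 90% power for N = 100, 94% against 67%. The Wilson lower bound is

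L = [p + z²/(2n) − z√(p(1−p)/n + z²/(4n²))] / (1 + z²/n), z = 1.96.

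Success needs 77/100 (L = 67.8%; 76/100 gives 66.8%). Exact power at 94% exceeds 99.99%, so the statement holds. For 60 subjects success needs 48/60 (L = 68.2%; 47/60 gives 66.4%).

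**Size for SVR.** One masked failure adds 1/100 = 1.0 point, or 1/60 = 1.7 points in China. At 94/100, L = 87.5%. If three of the six failures were masked, 97/100 gives L = 91.5%. Both are far above 67%.

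If an assumed share f of true failures is masked, the apparent rate is p + f(1 − p):

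| f | Apparent rate at true 94% | Apparent rate at true 67% | Chance of success at true 67%, N = 60 | Same, N = 100 |
|---|---|---|---|---|
| 0 | 94.0% | 67.0% | 1.9% | 1.9% |
| 5% | 94.3% | 68.7% | 3.6% | 4.3% |
| 10% | 94.6% | 70.3% | 6.3% | 8.5% |
| 20% | 95.2% | 73.6% | 16.4% | 25.9% |

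The success columns treat one test alone. For China, SVR24 is tested only after SVR12 succeeds, which can only lower the chance of a false SVR24 claim.

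**The case against.** A completer-only relapse rate is a recognised summary, and the protocol uses it consistently in the synopsis, 8.1.2.2 and 8.1.2.5. That stands, and it is a reason to keep that rate. It does not remove the conflict with 5.1.3 and 5.4.1.1, nor the gap left for early stoppers.

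On SVR, no sentence says that values on another regimen are accepted, the Section 5.5.1 sentence concerns resistance monitoring, and an analysis plan not shown could add an exclusion. This has weight. But the protocol itself fixes the SVR definition and the imputation order, and those rules applied as written give the wrong classification. Some protection exists: a completer's confirmed relapse stays in the relapse endpoint, and the first sensitivity analysis in 8.1.2.3 fills an empty window from the last earlier value. That analysis does not help when the value in the window was itself obtained on another regimen.

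Three stronger readings are tempting but not supported:

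- *Early-stopper relapses vanish from the primary analysis.* They do not. They stay in the ITT population as non-responders unless masked by the second problem.
- *Every misclassification favours the regimen.* Dropping early stoppers who do not relapse raises the reported rate slightly (2/95 against 2/100), and no figure in the protocol shows that early stoppers relapse more often.
- *Single values are treated more strictly on treatment than afterwards.* The rule that a single value "followed by lost to follow-up will be considered a rebound" belongs to an additional endpoint in 8.1.2.5. The secondary on-treatment failure endpoint requires confirmed values for rebound, as the relapse endpoint does.

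**Conclusion.** Both parts hold. The first is a direct conflict within the protocol: confirmed relapse after early stopping meets the general definition but enters no relapse rate, so the secondary endpoints together can understate virologic failure. The second follows from applying the SVR and imputation rules literally, and it touches a China primary endpoint.

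The practical size is modest. Under assumed counts, reported relapse is about 2% where the general definition gives 3% to 7%; if no early stopper relapses there is essentially no difference. For SVR, masking 5% to 20% of failures adds 0.3 to 1.2 points at a true 94%. A reader might infer that the superiority conclusion is at risk, but at the planned rate it is not: about 94 of 100 responders are expected and 77 suffice. The error inflation in the table needs a true rate near 67% together with the assumed masking. The change should be made, but the trial's main conclusion does not depend on it if SVR is near the planned rate.

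**What to change.** In Section 8.1.2.2 and the synopsis, report confirmed relapse by post-treatment Weeks 12 and 24 among all dosed subjects with HCV RNA below LLOQ at the final treatment visit, whatever the treatment duration, alongside the completer-only rate. This brings the endpoints into line with 5.1.3 and 5.4.1.1.

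In Section 8.1, state that HCV RNA values on or after the start of any other anti-HCV therapy are not used for SVR, for flanking imputation or for later-value imputation. Such subjects count as non-responders at that time point unless SVR there was already shown before the new therapy began.

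The cost is analysis wording only. Sample size, visits and data collection do not change, because post-treatment HCV therapy is already recorded. The reported SVR may be slightly lower, and the all-subject relapse rate may be less favourable than the completer rate.
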